#### **Long-term Assessments (same methods used pre-surgery):**

(1) **Pain Intensity:** NRS of the operated knee will be obtained by RN from the patients at the 3 wk, 6 wk, 3 mo and 6 mo scheduled visits.

(2) **Neurophysiologic Assessment** will be performed at the 6 mo scheduled visit.

(a) *Examination of the knee for peripheral neuropathic pain (StEP)*

(3) **Psychosocial Measures:** Beck Depression Inventory will be administered at 6 mo by RN.

(4) **Functional Measures:** ROM, WOMAC and SF-36 questionnaires will be administered at 3 wk, 6 wk, 3 mo and 6 mo.

(5) **Skin Temperature:** Skin temperature will be performed at 6 months

**Patients who have NRS $\geq$ 4 at three wks and beyond:** For patients having NRS $\geq$ 4 at 3 wk and beyond, the oral opioid regime will be continued. If the hydrocodone/acetaminophen regime does not maintain a NRS $<$ 4, then oral long-acting opioids such as time-release oxycodone 10 mg twice/day will be prescribed. The purpose of closely following the analgesics and NRS for the study patients is to ensure that at the 6-mo time point the analgesic consumption is within a standard protocol for all patients, whether they do or do not have PPP. Patients who have persistent pain at the 3 and 6-mo visits will be evaluated by the orthopedic surgeon for prosthetic-related failure. An examination will be performed to evaluate instability of the tibial femoral joint or patellar maltracking. Plain radiographs will be reviewed by the orthopedic surgeons (Co-investigators) for evidence of prosthetic loosening, malposition and patellar maltracking, as well as overall axial alignment to ensure coronal alignment is within the range of neutral to 10 deg of valgus. If this evaluation is negative, an erythrocyte sedimentation rate (ESR) and C-reactive protein (CRP) measurement will be obtained as a screening tool for infection. If these indices are abnormal (ESR $>$ 30 mm/h; CRP $>$ 10 $\mu$ g/mL), an aspiration of the knee will be performed, including a synovial fluid white blood cell count with differential and culture to rule

out infection. These parameters are based on previous work by [name] (Co-investigator) in this specific topic.

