model fit will be evaluated for all models. **Moderating** effects will be tested using model building with predefined interactions for linear or logistic models.

Due to the extensive monitoring designed into our protocol we do not expect a large amount of missing data; however, the missing data that does arise will be handled using multivariate multiple imputation. Data not assumed to be missing at random, will be evaluated for systematic effects using sub-groups stratification. Statistical analyses will be performed using SAS version 9.1 (SAS Institute Inc, Cary, NC) or SPSS (SPSS for Windows, Rel. 16.0.1. 2007. Chicago: SPSS Inc.), with statistical significance determined with a Type I error threshold of  $\alpha = 0.05$ . For continuous outcome mediation analysis we will use a SAS macro (INDIRECT macro) and for dichotomous outcomes the SPSS macro version (INDIRECT macro) will be used, as the SAS macro version does not allow for dichotomous outcome variables.

**Primary endpoint:** The *primary endpoint* for the **Primary Aim** will be the incidence of PPP after TKR (similar to our power analysis), evaluated at 6 mo. For the **Secondary Aims**, the *primary endpoint* will be functional outcomes (ROM, WOMAC, SF-36,).

**Secondary endpoints:** The *secondary endpoint* for the Primary and Secondary Aims will examine additional parameterizations of PPP at 6 mo (NRS pain non-dichotomous, StEP neuropathic pain examination). Use of raw NRS pain scores may highlight functional (e.g. linear) relationships between pain and the predictive factors. Analysis will be performed as described for the primary outcome variable (incidence of PPP) but with the re-parameterized outcome variable and different model assumptions, depending on distributional properties. Each re-parameterization will be evaluated with respect to and compared with the primary outcome.

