**Covariates:** Preoperative covariates included are as follows: age, weight/BMI, OA severity and ASA status. Perioperative covariates include: postoperative analgesic consumption and duration of surgery. Complications after TKR will be recorded and included as a summed incidence. Patient questionnaires of drug use in the first three wks postoperatively will be converted to daily morphine equivalents and included as a covariate in the predictive models. Although the protocol stipulates uniformity in medication use during the acute postoperative period, once the patient leaves the hospital, their analgesic use over the next 6 mo cannot be rigidly controlled. To reduce variation we will prescribe analgesics as needed (per protocol above mentioned) and will remain in contact with the patients to record additional medication.

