### **Detailed Analyses:**

**Primary Aims:** are to investigate the relationships of *risk factors* and the development of PPP at 6 mo post-TKR, through independently predictive (for clinical prediction models, Hypothesis 1) and mediated models (to reveal underlying mechanisms, Hypothesis 2). These risk factors are preop thermal pain sensitivity; anxiety and catastrophizing; postop area of secondary mechanical hyperalgesia and pain intensity.

A. **Independent Risk Factors:** Risk factors will be individually predictive of the PPP (primary endpoint):

*Hypothesis 1 is that greater (↑) preop pain sensitivity, higher levels of preop pain anxiety and catastrophizing, larger areas of secondary hyperalgesia post-TKR and higher postop pain intensity will independently predict increased incidence of PPP at 6 months post-TKR.*

- 1) **Pain Intensity:** Expected Result: (Hypothesis 1): Higher postop pain intensity (↑), will independently predict increased incidence of PPP at 6 mo post-TKR (ex. ↑ postop NRS → ↑ PPP incidence).
- 2) **Neurophysiologic:** Expected Result: (Hypothesis 1): Greater preop pain sensitivity (↑) and larger areas of secondary hyperalgesia ( $\text{cm}^2$ ) post-TKR will independently predict increased incidence of PPP at 6 mo post-TKR (ex. ↑ preop thermal pain sensitivity → ↑ PPP incidence).
- 3) **Psychosocial:** Expected result: (Hypothesis 1): is that greater (↑) catastrophizing (PCS score) will independently predict increased incidence of PPP at 6 months post-TKR (ex. ↑ PCS score → ↑ PPP).
- 4) **Demographics:** Expected result: Patients 65-85 yrs will have a lower incidence of PPP than patients 18-64 yrs.

B. **Mediation Models:** Effects of preoperative factors on development of PPP occur through interrelated neurophysiologic mechanisms:

*Hypothesis 2 is that the effects of preoperative factors on development of PPP occur through interrelated neurophysiologic mechanisms. Thus, it is expected that the area of secondary hyperalgesia post-TKR will mediate links between preoperative pain sensitivity and PPP incidence, as well as mediate links between pain anxiety/catastrophizing and PPP incidence at 6 mo after TKR.*

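### The 6-month ROM, WOMAC, SF-36 and StEP analyses do not prespecify adjustment for the preoperative value of the same measure

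*Combined protocol and SAP*

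**What the plan says.** The study calendar marks functional and neurophysiologic tests both before surgery and at 6 months. The pre-surgery assessments describe StEP, ROM, WOMAC and SF-36, and the follow-up section is headed "Long-term Assessments (same methods used pre-surgery".

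Under Primary endpoint, the endpoint for the Secondary Aims "will be functional outcomes (ROM, WOMAC, SF-36". No model is written for these scores: the Secondary Aims part of Detailed Analyses deals only with age as a moderator for PPP.

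Under Secondary endpoints, the plan lists "additional parameterizations of PPP at 6 mo (NRS pain non-dichotomous, StEP neuropathic pain examination" and then states: "Analysis will be performed as described for the primary outcome variable (incidence of PPP) but with the re-parameterized outcome variable and different model assumptions". That sentence governs the raw NRS score and StEP. It does not reach ROM, WOMAC or SF-36.

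Under Covariates: "Preoperative covariates included are as follows: age, weight/BMI, OA severity and ASA status". It continues: "Perioperative covariates include: postoperative analgesic consumption and duration of surgery", with summed complications and early opioid use added. Detailed Analyses gives the predictors: "These risk factors are preop thermal pain sensitivity; anxiety and catastrophizing; postop area of secondary mechanical hyperalgesia and pain intensity". The example prediction equation adds only age to such factors. Nowhere is a preoperative function or StEP value named as a covariate, and no change score is defined for these outcomes.

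**The concern.** The Significance section expects preoperative pain sensitivity and psychosocial factors to be linked to mobility and quality of life at 6 months, and calls these effects direct and independent. General statistical analysis likewise tests for independent association.

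Two links can produce such an association without any effect on what happens after surgery, and the plan itself makes both plausible:

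- **Risk factor to preoperative status.** The Significance section reports that catastrophizing in OA patients goes with higher pain and hyperalgesia, and that fear of movement may restrict the knee. WOMAC has a pain dimension, and StEP records hyperalgesia.
- **Preoperative status to 6 months.** The title of reference 15, a study of hip and knee replacement outcomes, says that preoperative function predicts the six-month result.

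If the preoperative value is left out, a risk factor takes credit for disability or sensory signs that were there before the operation. Variation that baseline could explain also stays in the error term.

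**Working it through.** **1. Is the preoperative value in any 6-month model?**

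| Outcome | Measured preop and at 6 months | Model written | Own preop value named |
|---|---|---|---|
| StEP | Yes | Yes, carried over from PPP | No |
| ROM, WOMAC, SF-36 | Yes | No | No |

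Four other places might have supplied it, and none does:

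- The introduction to the measures lets them serve as predictors or outcomes, depending on the hypothesis. This is a general permission and names no adjustment.
- OA severity is read from a radiograph, so it is at most a partial stand-in for disability.
- The mixed models in General statistical analysis are for the raw 6-month NRS.
- Modelling of change over time appears under Future Directions, and for risk factors.

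**2. How large could the effect be?** The plan states no figure for function or StEP that could be reproduced. Its sample size was set for PPP. The only input taken from it is the number of completers: 300 × (1 − 0.15) = 255.

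Assumptions, none of them in the documents: a continuous outcome; one risk factor in a linear model; no effect of the risk factor once baseline is known; correlation of risk factor with preoperative score a = 0.3 to 0.5; correlation of preoperative with 6-month score b = 0.3 to 0.5.

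- Apparent standardized effect without baseline: r = a × b.
- Rejection rate at two-sided 5%, by Fisher's z: the mean of the test statistic is m = atanh(r) × √(255 − 3) = atanh(r) × 15.87, and the rate is Φ(m − 1.96) + Φ(−m − 1.96).
- Explained variance that baseline adds to a model already holding the risk factor: b² − (ab)² = b²(1 − a²).

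| a | b | r = ab | m | Rejection rate | Variance added |
|---|---|---|---|---|---|
| 0.3 | 0.3 | 0.09 | 1.43 | 30% | 0.09 × 0.91 = 8.2% |
| 0.3 | 0.5 | 0.15 | 2.40 | 67% | 0.25 × 0.91 = 22.8% |
| 0.5 | 0.3 | 0.15 | 2.40 | 67% | 0.09 × 0.75 = 6.8% |
| 0.5 | 0.5 | 0.25 | 4.05 | 98% | 0.25 × 0.75 = 18.8% |

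Simulation (3,000 data sets per setting) gives the same unadjusted rates, and 4.8% to 5.8% with baseline in the model.

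**3. Sensitivity.** With a = 0.2 and b = 0.3, r = 0.06 and the rejection rate is 16%. With a = 0.4 and b = 0.6, r = 0.24 and the rate is 97%. Simulated rates with baseline included were about 5% to 6%.

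**The case against.** **The plan is silent on baseline values; it does not rule them out.** This stands. A reader might infer that the sponsor decided to model function without baseline. The documents do not support that: no function model exists, the covariate list is not tied expressly to function or StEP, and the measures may in general serve as predictors. But the preoperative list is worded as complete, and a general permission leaves the choice to be made after the data are seen.

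**The target is 6-month status, not recovery.** This stands in part. Hypothesis 1 is meant for clinical prediction, and for 6-month status an unadjusted association is real. The rejection rates above are errors only against the null of no effect beyond baseline. The plan, however, also claims independent and mediated effects, and for those the distinction matters. Preoperative function would also be an obvious candidate for prediction.

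**Baseline may lie on the causal path.** This stands. If catastrophizing worsens function before surgery, adjustment removes that part of its total effect. It is a reason to report both models, not to omit the adjusted one.

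**The illustration is simple.** This stands. It omits the listed covariates, the other risk factors and the step-down Bonferroni correction. StEP has a cut-off of 4 or more, so its model may be logistic, which would change the numbers though not the direction. The assumed correlations are least supported for StEP, because the 6-month examination follows surgery on that knee. Multiplicity correction does not remove confounding.

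**Conclusion.** The point holds as a gap in specification. All four measures are available before surgery, and the plan commits no 6-month model to the preoperative value of its outcome. Claims of independent association with 6-month function or StEP therefore cannot be told apart from differences already present.

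The size is unknown. The range of 0.09 to 0.25 for the apparent effect, and of 30% to 98% for rejection, rests wholly on the assumed correlations and on a one-predictor linear model under the null of no effect beyond baseline. A reader might take it as the error rate to expect in this study; the documents give no correlations that would support that. A reader might also take b² (9% to 25%) as the variance gained. With the risk factor already in the model the gain is 6.8% to 22.8%, and less if the listed covariates share variance with baseline. Measurement error in the preoperative score would leave some bias even after adjustment.

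The point concerns the function and StEP analyses only. It gives no ground for questioning the primary PPP analysis or the sample size.

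**What to change.** In the Primary endpoint, Secondary endpoints and Covariates paragraphs:

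1. Write out the models for 6-month ROM, WOMAC and SF-36.
2. State that each 6-month ROM, WOMAC, SF-36 and StEP model includes the preoperative value of the same measure, kept in the model and exempt from backward selection at P<0.05.
3. Report the model without the preoperative value alongside, labelled as the association with 6-month status.

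The cost is SAP wording and one parameter per model, with no new data. The adjusted estimate will exclude any part of a risk factor's effect that had already acted through preoperative status, and the text should say so.

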***We submit that any strategy used to investigate risk factors for PPP must not only consider multiple risk factors across various domains, but must also examine how these risk factors inter-relate, interact and combine over time to predict and/or influence the incidence of PPP following surgery.*** Doing so would greatly facilitate the development of predictive models for PPP after surgery, improve the capacity to identify patients during the preoperative period who are at highest risk, and thus promote work on interventions to prevent this chronic condition. Our proposed study will undertake such a multi-factorial prospective approach.

**Risk Factors for PPP:** Preoperative pain intensity has been implicated as a possible factor for PPP after TKR in some studies. These studies utilized validated patient measures of pain such as the numerical rating scale of pain intensity, Short Form 36 health survey, Western Ontario and McMaster Universities Osteoarthritis Index, and Knee Society Score. Recent studies have used experimental pain stimuli (e.g. heat) to quantify pain sensitivity and to predict acute postoperative pain. *The value of preoperative pain sensitivity in predicting outcomes will be enhanced in our proposed study by including both self-report of knee pain and sensitivity to experimental pain.* To our knowledge, no published studies have used a multi-domain approach to quantify pain intensity and sensitivity prior to TKR. The significance of our project will be increased by our ability to examine the degree to which pain sensitivity to experimental pain stimuli – distinct from patient self-report of perceived knee pain – predicts the incidence of PPP 6-mo post-TKR.

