## Approach

**Overall Strategy:** The primary aim of this application is to investigate relationships of risk factors to the development of PPP at 6 mo following TKR, through independently predictive and mediated models. These risk factors are preoperative thermal pain sensitivity, pain anxiety and catastrophizing; postoperative area of secondary mechanical hyperalgesia or hypoalgesia (numbness) and pain intensity. **PPP** for this study will be defined as "**pain in the operated knee at six months after TKR, with other causes of pain excluded and reported intensity on 0-10 NRS scale of  $\geq 4$ .**" The study will also evaluate the relationship of PPP incidence with the severity of functional impairment. This is a single-site prospective clinical investigation of 300 consented OA patients undergoing primary, unilateral TKR. Although we realize the importance of genetic susceptibility on the development of PPP, the complexity of determining the multiple genes that may contribute to this condition is beyond the scope of this proposal. However, prior to surgery we will obtain a blood sample (8.5 mL) from all patients, process it for DNA analysis, and store at -80° C for future studies by [name], NINR (letter of support) to screen for genetic predictors of PPP, such as COMT and GCH1. We will also obtain three blood samples (5ml each) for RNA analysis. In a previous IRB approved study, we also obtained blood samples for RNA analysis prior to hip replacement surgery and 24 hours afterward and found that IL18R1 was up-regulated while IL-8RB was down-regulated and may be related to the normal acute post

operative inflammation. However, we now need to examine the changes in cytokine gene expression in the TKR patients. All of the blood samples will be sent for analysis to [name] laboratory. The patients' genetic information will stay confidential, and will be identified by a study number, and not a name. This information will not be disclosed to any other third party. Personal data will be stored at Rush University Medical Center. The samples sent to [name] laboratory will be appropriately coded so that the patient's name does not appear on the samples. Data will be kept for 1 year from the time the last patient is enrolled in the study.

Study Calendar	Preop	Post-Incision				Post-operative			
		24h	36h	48h	72h	3 wk	6 wk	3 mo	6 mo
General Physical Examination	X					X	X	X	X

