**Enrollment & Pre-surgery Assessments:** Prior to pre-operative assessments, up to 8 weeks prior to surgery, written informed consent will be obtained. Demographic data such as age, BMI, ASA status and a physical examination will be performed by PI and RN. All of the assessments below will be coordinated by the RN, in conjunction with the routine preoperative laboratory tests for undergoing TKR. We will obtain an 8.5mL DNA blood sample as well as a 5mL RNA blood sample. A knee radiograph (AP and lateral weight bearing views) will also be reviewed by the study's orthopedic surgeon to determine OA severity (scale) and documented. Patients will be instructed to discontinue non-steroidal anti-inflammatory drugs (NSAIDs) a wk prior to surgery as routine clinical practice. A prescription for tramadol hydrochloride 50 mg tablets with a maximum of 3 tablets /day will be provided to the patients to be taken if the pain in the knee is of moderate-to-severe intensity prior to the surgical date.

All measures selected for this study are established, reliable and validated and listed in order of importance. These measures will be classified into Pain, Neurophysiologic Assessment, Psychosocial and Functional test categories and may be used as predictors, mediators, moderators, or outcome measures, depending on specific hypotheses, and will be assessed at various time points as shown in the study calendar.

**(1) Pain Intensity: Numerical Rating Scale (NRS) of pain intensity:** The NRS score has been selected as the primary instrument to quantify pain intensity. Subjects will be presented by the RN with 11-point NRS, (0 = "no pain" and 10 = "worst pain imaginable"), accompanied by the instructions "Please rate your pain by

indicating the number that best describes your pain on average in the past 2h of the affected knee joint." The NRS will be evaluated at rest, and also with movement (patient-initiated flexion). The NRS is used extensively in clinical trials reported in the orthopedics, pain and surgical literature. Within the pain literature, a NRS <4 is considered mild pain, while a NRS ≥4 is moderate-to-severe pain.

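### Preoperative knee pain is collected and named as a possible risk factor, but no specified model includes it, so the thermal-sensitivity models, chiefly the Hypothesis 2 mediation model, do not separate thermal sensitivity from existing knee pain

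*Combined protocol and SAP*

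**What the plan says.** Under Risk Factors for PPP in the Significance section, the protocol states: "Preoperative pain intensity has been implicated as a possible factor for PPP after TKR in some studies". It then says the value of preoperative pain sensitivity will be enhanced by "including both self-report of knee pain and sensitivity to experimental pain", and describes sensitivity to experimental stimuli as "distinct from patient self-report of perceived knee pain".

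The knee rating is collected. The study calendar marks pain intensity at the preoperative visit, and Enrollment & Pre-surgery Assessments adds: "The NRS will be evaluated at rest, and also with movement (patient-initiated flexion". The patient is asked for "indicating the number that best describes your pain on average in the past 2h of the affected knee joint". The same section says the measures "may be used as predictors, mediators, moderators, or outcome measures, depending on specific hypotheses".

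The analysis text is narrower. Overall Strategy says: "These risk factors are preoperative thermal pain sensitivity, pain anxiety and catastrophizing; postoperative area of secondary mechanical hyperalgesia or hypoalgesia (numbness) and pain intensity". Covariates says: "Preoperative covariates included are as follows: age, weight/BMI, OA severity and ASA status". Under Detailed Analyses, the pain-intensity factor in Hypothesis 1 is postoperative, and Hypothesis 2 runs from the thermal score through the area of secondary hyperalgesia to PPP. The example prediction equation has age, preoperative pain sensitivity, hyperalgesia area, postoperative NRS, trait anxiety and catastrophizing.

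**The concern.** A patient whose knee already hurts more may rate a heat probe as more painful, may develop a larger hyperalgesic area after surgery, and may be more likely to have PPP at 6 months. If so, part of any thermal association would belong to knee pain the patient brought to the operation. The plan collects the variable that could tell the two apart, but no named model uses it.

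Two claims are at stake, unequally. Hypothesis 2 is offered to reveal mechanism, and a common cause of the predictor and the mediator can produce an indirect path that does not exist. Hypothesis 1 says each factor predicts PPP independently. That wording is affected if it is taken to mean apart from knee pain, but Detailed Analyses ties Hypothesis 1 to clinical prediction, where a correlated marker remains a legitimate predictor.

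**Working it through.** **1. Where preoperative knee NRS appears.**
- Rationale (Significance): cited as a possible factor.
- Data collection (study calendar, pre-surgery assessments): collected at rest and with movement.
- Risk factors (Overall Strategy, Detailed Analyses): absent; pain intensity is postoperative.
- Covariates: absent. OA severity is graded from a radiograph, so it is not a substitute.
- Hypotheses 1, 2 and 4, and the example equation: absent.
- Omnibus models: no variables listed.

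The plan gives no figure for this point, so there is none to reproduce. The sizes below rest on assumed associations.

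**2. Inputs.** From the power section:
- Evaluable patients: 300 × 0.85 = 255.
- PPP incidence: 17.8%.
- Postoperative NRS: odds ratio 1.24 per point, SD 2.9, so 1.24^2.9 = 1.87 per SD.

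All associations of preoperative NRS and of the thermal score are assumed.

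**3. Hypothesis 2.** Let knee pain K drive both thermal score T and area A, each with correlation r, and give T no effect on A or on PPP. A and K each have odds ratio 1.5 per SD on PPP. A path is declared when T→A and A→PPP are both significant at two-sided 0.05. This joint test stands in for the bootstrap and Sobel methods in the plan.

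*T→A without K.* The correlation of T with A is r × r. With z = atanh(r²) × √(255 − 3):
- r = 0.2: z = 0.64, flagged in about 10% of trials.
- r = 0.3: z = 1.43, about 30%.
- r = 0.4: z = 2.56, about 73%.

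*A→PPP without K.* The coefficient is about ln 1.5 × [1 + r/(1 + r²)] = 0.483, 0.517 and 0.545. With a standard error near 0.18, z = 2.69, 2.87 and 3.03, and power is about 77%, 82% and 86%.

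*Both steps.* 0.10 × 0.77, 0.30 × 0.82 and 0.73 × 0.86 give roughly 8%, 25% and 63%. Simulation gave about 9%, 27% and 62%; repeat runs gave 7–9%, 25–27% and 62–63%. With K in both equations, T→A is flagged at its nominal 5%, so the joint rate cannot exceed about 5%. It simulated at 3–4%. These runs treat K as measured without error.

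**4. Hypothesis 1.** Logistic simulation with thermal truly null, postoperative NRS in the model, thermal/preoperative-NRS correlation 0.2–0.4, pre/post NRS correlation 0–0.5, and an unadjusted two-sided 0.05 test:

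| Assumed direct preoperative-NRS OR per SD | Spurious thermal OR per SD | Thermal flagged |
|---|---|---|
| 1.2 | 1.03–1.07 | 5–7% |
| 1.5 | 1.06–1.17 | 6–15% |
| 1.87–2.2 | 1.09–1.36 | 8–40% |

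With error-free preoperative NRS added, the rate is about 5% throughout. If the Bonferroni step-down covers the five Hypothesis 1 factors (assumed), the unadjusted-for-NRS rates are about 2–2.5%, 2–7% and 3–23%, against 1–2% with NRS added. Postoperative NRS removes the part of preoperative pain that acts through acute pain, but not a direct part.

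**The case against.** The best reply is that nothing bars the model. The measures section allows any measure to be a predictor, the omnibus models are open, the printed equation is only an example, and the term for preoperative pain sensitivity could be read to cover self-reported pain too. Part of this stands. A reader might infer that thermal sensitivity and knee pain can never be separated in this study; the documents do not support that, because the value is collected and its use is allowed. What remains is lack of commitment. The allowance depends on specific hypotheses, and none names preoperative NRS. Hypotheses 1, 2 and 4 illustrate sensitivity with the thermal score, and one merged term would not separate the two measures.

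A reader might also infer that the Significance section promises an adjusted analysis. The words "distinct from patient self-report of perceived knee pain" can equally describe how experimental sensitivity differs as a measure. The firmer commitment is to include both measures, which falls short of promising to adjust one for the other.

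Finally, the highest Hypothesis 1 rates come from an extreme corner. The 40% needs a thermal correlation of 0.4, no correlation between pre- and postoperative NRS, and preoperative pain stronger (odds ratio 2.2) than acute pain (1.87). Letting catastrophizing correlate 0.4 with preoperative NRS (assumed) lowers that cell to about 30%, or from 22% to 17% after step-down. This objection stands, and the 40% should not be read as an expected rate.

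**Conclusion.** The point holds as a gap between the stated rationale and the specified models. It is a cheap improvement, not a fatal flaw. Its weight lies in the Hypothesis 2 mechanism claim, where the false-path rate is about 9% to 62% without preoperative NRS and 3% to 4% with it. That range requires knee pain to drive both thermal score and area, and every correlation and odds ratio behind it is assumed. Hypothesis 1 is less exposed: 5–7% at odds ratio 1.2, which is negligible, 6–15% at 1.5, and more only under stronger assumptions. A reader might infer that the prediction equation is invalid; it is not, because predictive use needs no confounder control. The documents give no thermal–knee-pain correlation and no effect of preoperative NRS on PPP, so the true size is unknown and may be nil.

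**What to change.** Add preoperative knee NRS to the preoperative covariates, naming one rating (rest or movement) in advance. State that the NRS-adjusted model is the test for the Hypothesis 2 thermal mediation model, and for any Hypothesis 1 claim that thermal sensitivity predicts PPP apart from knee pain. Report the unadjusted thermal estimate as a sensitivity analysis, because knee pain may itself partly reflect pain sensitivity and adjustment could over-correct. Offer preoperative NRS as a candidate in the prediction equation.

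No new data are needed. The costs are:
- **One more term.** Expected events are 255 × 0.155 to 255 × 0.178, or about 40 to 45. The plan names about 13 terms (8 covariates, 5 risk factors), so events per term fall from 3.0–3.5 to 2.8–3.2.
- **Precision.** The thermal standard error rises about 2% (0.180 to 0.184, correlation 0.2) to 13% (0.180 to 0.203, correlation 0.4). If thermal truly has odds ratio 1.5 per SD and preoperative NRS has no effect, power falls from 63% to 62% or from 62% to 55% respectively.
- **Incomplete control.** The NRS is a single 2-hour rating. At an assumed reliability of 0.5–0.7, the Hypothesis 1 thermal false-positive rate after adjustment is still 4–15%. The plan should say that some confounding may remain.
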